#### **Statistical Methods**

A general description is included here for the investigator. A detailed Statistical Analysis Plan will be submitted to the IND prior to unblinding the database for Part 2.

#### Sample Size

The Part 1 sample size was derived empirically from experience with previous single ascending dose clinical studies in other disorders and is deemed appropriate to achieve the study objectives.

The Part 2 sample size was selected to ensure adequate power for detecting treatment-related change in bilateral UEMS (Score from 0 to 50).

A 5-point difference, between the treated and placebo groups, in the change from baseline to 6 months in bilateral UEMS is considered clinically meaningful. Analysis of historical data for cervical SCI patients for the period between ~6-12 months following acute SCI indicates a standard deviation of bilateral UEMS change over 6 months to be around 3 to 4 points.

With a sample size of 12 subjects per active and placebo group, Part 2 of the study has 80% power with Type I error of  $\alpha$ =0.05 (two sided), assuming a 5-point difference as indicated above, and with a common standard deviation within each treatment group of approximately 4 in the change from baseline to 6 months in bilateral UEMS.

Accounting for uncertainties in the assumptions based upon historical data used to extrapolate for estimating the sample size in this study and the need for estimation of missing data a sample size of approximately 16 subjects per treatment arm (32 total) will be randomized.

#### Stages of Analysis

The analysis for this study will be performed in three stages, with the first analysis performed upon completion of the clinical portion of Part 1, the second analysis (including the core efficacy assessment) performed upon completion Day 169 of Part 2 (ie, after all subjects have completed through Study Day 169), and the final analysis performed upon completion of the post-treatment follow-up phase of Part 2 (Day 253). The methods applied to each analysis will be consistent with the objectives of the study.

The blind will be maintained for all blinded study personnel (including investigators and subjects) through the completion of Day 169 of Part 2. After completion of Day 169, designated sponsor staff and external consultants/contractors required to perform the analysis will be unblinded to the treatment allocations in order to complete data analysis though Day 169. The blind will be maintained for site investigators and subjects through completion of Day 253 unless the blind must be broken sooner for safety or regulatory reasons.

#### General Methods

Data will be tabulated using both descriptive and inferential statistics where specified.

- For Part 1, data will be tabulated by dose cohort as well as pooled (all subjects combined), and no inferential statistics are planned.
- For Part 2, data will be tabulated for each treatment group separately (placebo and AXER-204) to allow for visual inspection of outcomes between the arms. Inferential statistical comparison of the treatment groups is planned.

For both Parts, all data collected will be included in by-domain data listings, sorted by subject number and time point, or as appropriate.

No hypothesis testing will be performed for demographics, background, or safety data.

Continuous data will be summarized by presenting the number of subjects (n), means, mean changes from baseline, mean % changes from baseline (where appropriate), standard deviations, minimum, First quartile (Q1), median, third quartile (Q3), and maximum values. The number of subjects with missing data will be indicated.

Categorical data will be summarized by presenting the number of subjects (n), the number of subjects with missing data as well as counts and percentages in each of the categories. Percentages will be based upon the number of subjects with available data.

When inferential testing is applied to all efficacy assessments, dichotomous/binary categorical efficacy endpoints will be assessed via a 2-sided Fisher's Exact test or Chi-square test as appropriate. Continuous efficacy endpoints will also present least-squares means and p-values from hypothesis testing of efficacy endpoints using mixed-effects model for repeated measures (MMRM).

Additional details will be included in the statistical analysis plan (SAP) which will be finalized prior to unblinding Part 2 of the study and any amendments to it made prior to locking the database and unblinding the study.

#### Handling of Missing Data

Every attempt will be made to collect all protocol required data at each time point.

Imputations will only be performed for efficacy data and for missing or partial dates, missing severity or relationship to investigational product. Missing AE or CM dates and missing severity or relationship to study drug will always use a conservative approach. Details will be included in the SAP.

For subjects who discontinue treatment (for any reason), subjects will continue to be followed and key efficacy endpoints and safety data collected where possible.

#### Analysis Populations

Safety Population: Safety outcomes will be assessed for all subjects who are given at least one dose of investigational product.

Full Analysis Set (FAS) Population: Efficacy outcomes will be evaluated using the FAS, defined as all subjects randomized, treated with at least 1 dose of investigational product, and with at least one post-baseline assessment of efficacy.

Per Protocol Population: The per protocol population will be a subset of FAS and include subjects who received at least 80% of study drug and have no major protocol deviations that would impact efficacy assessment.

#### Alpha Level Considerations

All inferential testing will be performed using two-sided 5% Type I error ( $\alpha$ ), and therefore 2-sided p-values  $\leq 0.05$  will be considered statistically significant in this study.

The first hypothesis test will be the key secondary efficacy endpoint of change in bilateral UEMS from baseline to Study Day 169 using the MMRM model as detailed below. Additional secondary efficacy endpoints tested will be the change in GRASSP prehension performance from baseline and slope to Study Day 169 and of change in SCIM self-care from baseline to Study Day 169.

#### Efficacy Endpoints

Changes from pre-treatment to each on-treatment time point will be calculated, with the primary time point at Day 169. Shifts over time in ordinal endpoints will be presented, with comparisons between treatment groups assessed using a CMH row mean scores statistic at each time point. Slope of change will also be evaluated.

#### Safety Endpoints

Changes from pre-treatment will be calculated in a similar fashion as for the efficacy endpoints, but no inferential statistics will be provided for safety endpoints. Shifts from baseline in electrocardiogram (ECG) will be tabulated for heart rate and QTcF. Other endpoints will be assessed according to the scale of the variable.

Pharmacokinetic Endpoints

Concentration data in both blood serum and in CSF will be assessed descriptively over time. Correlation with efficacy and safety outcomes may be performed, as the data warrant.

#### Potential Open-Label Extension Study

The sponsor may, pending data outcomes from this current study, initiate an open-label extension study at a later date. This study would provide subjects who participated in Study RNX-AX204-101, during either Part 1 only and those receiving placebo in Part 2, the potential opportunity to participate in a repeat-dose study with AXER-204.

Initiation of the open-label extension study will be contingent on satisfactory results from the current clinical study (Part 1 and Part 2) supportive of continued development, funding, and the requisite regulatory and IRB approvals.

#### Protocol RNX-AX204-101

Table 5:Part 1 Schedule of Events (Study RNX-AX204-101)1

Study Phase	Screening		In-Clinic	Treat	tment			Post-Treatment Follow-Up			
Study Day	-84	1		2	3	4	5, 6, $7^2$	8	15	29/ET 	
Sound Duy	through -1	Pre-Dose	Post	1 -	•		c , c , .	± 1 days	$\pm 3$ days	$\pm 4$ days	
Visit Number	1	2					Phone Call 	3	4	5	
Informed consents (Main & Biobank)	Х										
Register Subject/Contact EDC/Assign Subject ID	Х										
Inclusion & Exclusion Criteria	Х	X									
Instructions for potential washout period for concomitant medications and for alcohol use	Х										
Urine sample for drug screen 	Х										
Medical/Disease History	Х	Х									
Full Physical Examination & Ht/Wt	Х									Х	
Demographics	Х										
Vital signs (BP, pulse, RR or pulse ox, oral temp) 	Х	Х	Х	Х	Х	Х		Х	Х	Х	
ECG 	Х	Х	Х			Х					
Serum pregnancy, chorionic gonadotropin	Х										
MRI 	Х										
ISNCSCI assessment, including AIS (Clinician Assessed)	Х									Х	
SCIM III self-care and mobility subscores (Clinician Assessed)	Х									Х	
GRASSP (Clinician Assessed)	Х									Х	
Admission/Discharge to/from Clinic		Admit				Discharge					
Physical Examination (abbreviated)		Х				X					
CSF collection (for PK assessment) 		Х		Х		Х		Х		Х	
Dosing of Investigational Product		Dosing									
Study Drug Accountability			Х								
Serum (for PK and ADA assessment) 		Х	Hr 1, 6, 12	Х		Х		Х	Х	Х	
Modified Ashworth Scale (Clinician Assessed)	Х									Х	
SF-36 v2 Health Survey (Subject Reported)	Х									Х	
Neuro-QOL v1.0 – Upper Extremity Function (Fine Motor,	Х									Х	
ADL) (Subject Reported)											
Brief Pain Inventory (Subject Reported)	Х				1					Х	
ISAFSCI (Clinician Assessed)	Х				1					Х	
Clinical laboratory sample collection 	Х	X		Х	Х	X			Х	Х	
Viral Serology 	Х				1					Х	
Urinalysis	Х				1					Х	

Study Phase	Screening		In-Clinic '	Treat	ment		Post-Treatment Follow-Up			
Study Day	-84	1		2	3	4	5, 6, 7 	8	15	29/ET 
	through -1	Pre-Dose	Post				- ) - )	±1 days	± 3 days	± 4 days
Visit Number	1	2					Phone	3	4	5
							Call 			
Urine pregnancy test 		Х								Х
Prior and Concomitant Medications	Prior					Conce	omitant (O	n-going)		
Adverse Events 			Treatment-Emergent (On-going)							
Serious Adverse Events	Pre-		Treatment-Emergent (On-going)							
	Treatment						•			

<sup>1 Abbreviations: AE = adverse events, ECG = electrocardiogram, EDC = electronic data capture. ET = early termination. ID = identification, PK = pharmacokinetic, SAE = serious adverse event

 Vital signs (blood pressure, pulse rate, respiratory rate or pulse oximetry, and oral body temperature) will be measured after the patient has been in a sitting or recumbent position for 5 minutes. Frequency noted below:

Screening visit - Once

 MRIs will be read by a sponsor-arranged expert prior to subject enrollment into the study

<sup>2 Note: Day 7 phone call may be skipped if Day 8 visit actually occurs on Day 7.

<sup>3 ET: early termination. Subjects who terminate the treatment prematurely (including those withdrawn from the study) should have all assessments performed according to the protocol. However, subjects who discontinue from the study may only have assessments performed per the ET visit.

<sup>4 Phone calls from the site to the subject will be made each day (Study Days 5, 6, and 7) after discharge from the clinic. Subjects will be queried for general health.  Urine testing for drugs of abuse will include the standard 9-drug panel (amphetamines, cocaine, marijuana, opiates, phencyclidine, barbiturates,

benzodiazepines, methadone, and propoxyphene). Patients must abstain from drinking alcohol and using recreational marijuana in US states where marijuana is legal, for at least 3 days prior to laboratory screening assessments on nominal Day-28.

Day 1 - Pre-dose, post-dose, then every 3 hours for 1st 24 h following dosing

Day 2-Day 4 (until discharge from the clinical unit) - Starting at 24 h post-dose, take vitals every 6 hours

Day 8, 29 - Pre-LP, post-LP, then every 3 hours until subject leaves the unit

Day 15 - Pre-blood draw

<sup>7 ECGs will be taken in triplicate, 5 minutes apart, will be obtained after the patient has been in a supine (resting) position for at least 5 minutes. At Visit 2, triplicate ECGs will be taken twice, pre-and post-dose. All ECGs will be read locally.

<sup>9 Serum samples collected and analyzed for ADA pre-dose and on Study Days 8 and 29

<sup>10 Clinical Laboratory Sample Collection: Sample collected on Study Days 1-4 are to be processed locally. INR/PTT is required prior to the Day 1 lumbar puncture procedure with repeat INR/PTT tests on subsequent Study Days at the direction of the Principal Investigator.

<sup>11 Infectious disease testing at Screening and Visit 5 (Study Day 29/ET) will include: HIV-1/HIV-2 antibody, hepatitis B surface antigen, hepatitis C antibody.

<sup>12 Urine Pregnancy Test will be performed locally on site for women of childbearing potential.

<sup>13 Adverse Events are only collected upon the start of study drug. Events occurring prior to this are to be reported as part of the subject medical history. However, SAEs are to be collected from the time of informed consent.

Study Phase	Screening		W	Trea indow a	tment P	hase -7 ± 5 da	vs			Follow-Up ± 7 days	
Study Day	-84 through -1	1	8 (±3 days)	21	42	63	84	104	137 Month 5	169 Month 6	253/ET  Month 9
Visit Number	1	2		3	4	5	6	7		8	9
Informed consents (Main & Biobank)	Х										
Register Subject/Contact EDC/Assign Subject ID	Х										
Inclusion/Exclusion Criteria	Х	Х									
Instructions for potential washout period for concomitant	Х										
medications and for alcohol use											
Demographics	Х										
Medical/Disease History	Х	Х									
Randomization		Х									
MRI 	Х										
Telephone call 			Х						Х		
Full Physical Examination & Ht/Wt	Х										Х
Physical Examination (abbreviated)		Х		Х	Х	Х	Х	Х		Х	
Vital Signs (BP, pulse, RR or Pulse Ox, oral temp) 	Х	Х		Х	Х	Х	Х	Х		Х	Х
ECG 	Х	Х		Х	Х	Х	Х	Х		Х	Х
ISNCSCI assessment including AIS	Х	Х		Х		Х		Х		Х	Х
GRASSP 	Х	Х				Х		Х		Х	Х
SCIM III self-care and mobility subscores		Х				Х		Х		Х	Х
Modified Ashworth Scale		Х								Х	Х
Brief Pain Inventory		Х								Х	Х
Neuro-QOL v1.0 – Upper Extremity Function (Fine Motor, ADL)		Х								Х	Х
SF-36 v2 Health Survey		Х								Х	Х
CUE-Q		Х								Х	Х
PGIC Chronic SCI		Х								Х	Х
ISAFSCI		Х								Х	Х
CSF collection (pre-dose if dosing visit) 		Х		Х	Х	Х	Х	Х			Х
Clinical laboratory sample collection (CSF)		Х		Х	Х	Х	Х	Х			Х
Dosing of Investigational Product		Х		Х	Х	Х	Х	Х			
Investigational Product Accountability		Х		Х	Х	Х	Х	Х			
Serum collection for PK (pre-dose & 4 h post-dose if dosing visit)		Х		Х	Х	Х	Х	Х		Х	Х
Serum collection for ADA (pre-dose if dosing visit)		Х		Х	Х	Х	Х	Х		Х	Х
Clinical laboratory sample collection 	X	Х		Х		Х		Х		Х	Х
Viral Serology 	X									Х	Х
Serum pregnancy, chorionic gonadotropin	X										
Urine Pregnancy Test 		X		X	X	Х	Х	X		Х	Х

Table 6:Part 2 Schedule of Events (Study RNX-AX204-101)1

Study Phase	Screening			Trea	atment P		Follow-Up				
			W	indow a	t Visits 3		± 7 days				
Study Day	-84	1	8	21	42	63	84	104	137	169	253/ET 
	through		(±3						Month 5	Month 6	Month 9
	-1		days)								
Visit Number	1	2		3	4	5	6	7		8	9
Urine sample for drug screen 	Х										
Urinalysis	Х	Х		Х		Х		Х		Х	Х
Prior and Concomitant Medications	Prior		Concomitant (On-going) Post-Trt								
Adverse Events 			Treatment-Emergent (On-going) Post-Trt								
Serious Adverse Events	Pre-Trt		Tr	eatment-l	Emergent	(On-goi	ng)			Post-Trt	

<sup>1 Abbreviations: ADA = anti-drug antibody, AE = adverse events, ECG = electrocardiogram, EDC = electronic data capture. ET = early termination. ID = identification, PK = pharmacokinetic, SAE = serious adverse event

benzodiazepines, methadone, and propoxyphene).

 Adverse Events are only collected upon the start of study drug. Events occurring prior to this are to be reported as part of the subject medical history. However, SAEs are to be collected from the time of informed consent.

<sup>2 MRIs will be run locally and findings read by a sponsor-arranged expert prior to subject enrollment into the study.

<sup>3 Telephone call to inquire about any AEs and determine if subject should come to clinic for evaluation.

<sup>4 Vital signs (blood pressure, pulse rate, respiratory rate or pulse oximetry, and oral body temperature) will be measured after the patient has been in a sitting or recumbent position for 5 minutes. Vitals will be taken pre-dose, post dose, then every 2 hours until subject leaves the unit

<sup>5 ECGs will be taken in triplicate, 5 minutes apart, and will be obtained after the patient has been in a supine (resting) position for at least 5 minutes. ECGs are taken pre-dose at visits where study drug is administered. ECGs will be read locally.

<sup>6 GRASSP prehension ability and prehension performance testing will be video recorded.

<sup>7 Remove aliquot for CSF labs before processing CSF for pharmacokinetics/biomarkers and biobank samples.

<sup>8 Clinical Laboratory Sample Collection: INR/PTT is required prior to the Day 1 lumbar puncture procedure with repeat INR/PTT tests on subsequent Study Days only if directed by the Principal Investigator. Screening labs must be completed within 28 days of enrollment.

<sup>9 Infectious disease testing at Screening, Visit 8 (Month 6) and Visit 9 (Month 9) will include: HIV-1/HIV-2 antibody, hepatitis B surface antigen, hepatitis C antibody.

<sup>10 Urine Pregnancy Test will be performed locally on site for women of childbearing potential.

<sup>11 Urine testing for drugs of abuse will include the standard 9-drug panel (amphetamines, cocaine, marijuana, opiates, phencyclidine, barbiturates,

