### 11.1.4. Post Treatment Follow-up Visits 3 & 4 (Study Days 8 and 15)

At Visit 3, Study Day 8, subjects' vital signs (BP, pulse, respiratory rate or pulse oximetry, and oral body temperature) will be obtained. Subjects will undergo a lumbar puncture and will have CSF collected for PK assessments. Blood samples will be collected and serum samples for PK assessments and presence of ADA will be obtained. Information on changes or newly administered concomitant medications as well as any new or ongoing AEs will be collected.

Subjects will be given instructions to return to the study site for the next visit and provided an appointment reminder card.

During Visit 4, Study Day 15, blood samples will be collected for clinical laboratory testing and serum samples obtained for PK analysis. Information on changes to ongoing and any new concomitant medication as well as any new or ongoing AEs will be recorded on the eCRF and in the patient's record.

At the completion of the visit, subjects will be given an appointment reminder card that contains the date and time of their next visit to the study site.

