### 11.1.5. Post Treatment Follow-up Visit 5 (Study Day 29/ET)

Visit 5 (Study Day 29/ET) is to be conducted on subjects who will be completing the study as well as those who terminate early or are withdrawn from the study.

At this visit, a full physical exam will be performed. The subject will be weighed and weight recorded on the eCRF. Vital signs (BP, pulse, respiratory rate or pulse oximetry, and oral body temperature) will be obtained. A urine pregnancy test will be obtained on all females of childbearing potential.

Subjects will undergo lumbar puncture for CSF collection for PK assessments. Blood sampling for laboratory testing including viral serology will also be obtained. Serum for PK and the presence of ADA will be analyzed. Urine sample will be obtained for urinalysis.

Information on changes or newly administered concomitant medications as well as any new or ongoing AEs will be recorded on the eCRF.

All scales should, if possible, be administered by the same clinician who administered the scales during the Screening period. These shall be completed in the order as noted in 11.2 and include the full ISNCSCI scale, SCIM III self-care and mobility scale, GRASSP, Modified Ashworth Scale, and autonomic evaluations as per ISAFSCI. Subjects will also be administered several questionnaires at this visit, including:

- BPI (Appendix 9)
- SF-36 v2 (Appendix 6)
- Neuro-QOL (Appendix 7)

Subjects' completion or termination from the study (in the case of subjects who terminate early from the study or who are withdrawn) will be recorded on the eCRF and in the subjects' record.

# 11.2. Part 2

Each investigator will be assigned a unique site code. This site code will be concatenated with the screening number to assure that each subject will be uniquely identified in the clinical database. Site numbering will begin with 01 preceded by the number 2, and screening numbers will begin with 001. As subjects are screened, the next subject qualified chronologically at a site will be assigned the next number in ascending numerical order. Thus, the subject identification number for the first subject screened at the first site will be 201-001. The first subject enrolled at the second site will be 202-001 and so on.

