### 14.1.5. Laboratory Assessments

The results of all laboratory tests required by the protocol will be recorded in the subject's eCRF. All clinically important abnormal laboratory tests occurring during the study will be repeated at appropriate intervals until they return either to baseline or to a level deemed acceptable by the Site Principal Investigator and the sponsor, or until a diagnosis that explains them is made. Abnormal laboratory test results that result in a change in study drug dosage or in discontinuation of the drug, or require intervention or diagnostic evaluation to assess the risk to the patient/subject, should be recorded as adverse events in the case report form. Investigators should review the CTCAE toxicity criteria that can be found at the following URL: https://ctep.cancer.gov/protocolDevelopment/electronic\_applications/docs/CTCAE\_v5\_Quick\_R eference\_8.5x11.pdf

All laboratory assessments will be collected as per the schedule of events (Table 5, Table 6).

The clinical laboratory tests analyzed in this study are provided in Table 12. The INRPTT, urine pregnancy testing and in-clinic safety laboratory tests requiring stat analysis will be processed locally. In addition, laboratory samples taken during Study Days 1-4 will be processed locally. All other laboratory tests will be analyzed by a central laboratory, **and the samples and urine samples will be collected and sent to the central laboratory on the day of** 

collection unless otherwise instructed. INR/PTT is required prior to the Day 1 lumbar puncture procedure with repeat INR/PTT tests on subsequent Study Days only if directed by the Principal Investigator. Clinical laboratory results will be reviewed by the study investigator when results are known prior to enrollment/randomization, and results available for each collection during the study including prior to discharge from the in-patient clinic in Part 1 of the study. During the course of the study, abnormal laboratory values should be repeated and subjects interviewed for evidence of clinical signs and symptoms consistent with the laboratory abnormality. Subjects with abnormal laboratories at screening can be rescreened (ie, lab repeated) for inclusion into the study within the 28-day screening window specified for labs. A Laboratory Manual will be provided separately for processing and shipping procedures.

Hematology	Serum Chemistry	
Hemoglobin	Glucose	Albumin
Hematocrit	Blood urea nitrogen	

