8.8.3 Laboratory Evaluations

All clinical laboratory data will be listed. Data for the following hematology, clinical chemistry, urinalysis and CSF laboratory (part 2 only) analytes (Table 7) will be summarized by dose cohort for Part 1 or treatment group for Part 2 and overall, and by visit. If data for any additional analytes are also recorded, then these will be listed only.

Table 7Clinical Laboratory Tests

Hematology	Clinical Chemistry	Urinalysis	CSF Analysis
			(Part 2)
Hematocrit Hemoglobin Mean corpuscular volume (MCV) Mean corpuscular hemoglobin (MCH) Mean corpuscular hemoglobin concentration (MCHC) Platelet count Red blood cell (RBC) count Red cell distribution width (RDW) White Blood Cell (WBC) Count including differential (neutrophils, lymphocytes, monocytes, eosinophils, basophils)	Alanine transaminase (ALT) Albumin Alkaline phosphatase Aspartate transaminase (AST) Bicarbonate Blood urea nitrogen Calcium Chloride Cholesterol Creatine kinase Creatinine Direct bilirubin Gamma-Glutamyl transferase (GGT) Glucose Lactate dehydrogenase Phosphorus Potassium Sodium Total bilirubin Total bilirubin Total protein Triglycerides Uric acid	Blood Glucose Ketones pH Protein Specific gravity Urine bilirubin	Total protein Glucose Red blood cells count White blood cells count Lymphocytes count Neutrophils count

All laboratory data will be reported in Conventional units. Out-of-reference-range values will be flagged as high (H) or low (L) in the listings.

For analysis purposes, values preceded by a "<" or a ">" sign (i.e. those below or above the limits of quantification) will be considered equal to the lower or upper limit of quantification, respectively.

Hematology and clinical chemistry data will be summarized for each dose cohort using standard descriptive statistics. Changes from baseline will also be summarized. Shift

CONFIDENTIAL

tables presenting movement in and out of reference range from baseline to each scheduled post-baseline visit will also be provided.

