Number and percentage of subjects having any clinically significant laboratory value during post-baseline will be summarized for hematology, clinical chemistry, and urinalysis analytes. In addition, number and percentage of subjects having new-onset potentially clinically significant (PCS) laboratory values will be summarized. A PCS value is defined as a value that is out-of-reference-range. New-onset value for an analyte is defined as a PCS value for a subject following initiation of study treatment for which the subject did not have a PCS value for that analyte prior to initiation of study treatment. The denominator for calculating the percentage is the number of subjects without any PCS values at baseline and with at least one post-baseline assessment.

For each laboratory analyte, the baseline value will be defined as last scheduled or unscheduled value collected prior to the first dose of study treatment. Assessments carried out on day of first study treatment administration are considered to have taken place before the study treatment administration, if the corresponding times have not been recorded. For post-baseline, only data from scheduled visits will be included in the summary tables.

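### Part 1 hematology and chemistry changes at Days 15 and 29 set central-laboratory results against a local-laboratory Day 1 baseline, so any offset between laboratories enters the mean change with no control arm to reveal it

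*Protocol*

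**What the plan says.** **Sampling.** The row "Clinical laboratory sample collection" in Protocol Table 5 (Part 1 Schedule of Events) is marked at Screening, Day 1 pre-dose, and Days 2, 3, 4, 15 and 29/ET. The text confirms the two late visits. Section 11.1.4 states "During Visit 4, Study Day 15, blood samples will be collected for clinical laboratory testing", and Section 11.1.5, for Day 29/ET, states "Blood sampling for laboratory testing including viral serology will also be obtained".

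**Which laboratory.** Footnote 10 of Table 5 reads "Sample collected on Study Days 1-4 are to be processed locally". Section 14.1.5 repeats the rule: "laboratory samples taken during Study Days 1-4 will be processed locally". It then adds "All other laboratory tests will be analyzed by a central laboratory". The exceptions to central analysis, besides Days 1-4, are INR/PTT, urine pregnancy tests and in-clinic safety tests needed urgently. The same section requires the results of all protocol-specified tests to be entered in the eCRF.

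**Analysis.** For laboratory analytes, SAP 8.8.3 states that "the baseline value will be defined as last scheduled or unscheduled value collected prior to the first dose of study treatment". For hematology and clinical chemistry by dose cohort, "Changes from baseline will also be summarized", and shift tables run from baseline to each scheduled visit. A potentially clinically significant (PCS) value is any value outside the reference range. The only rule on comparability is that conventional units are used.

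**The concern.** The baseline and the late follow-up values come from different laboratories. A method or calibration difference between a site laboratory and the central laboratory would appear in the tables as a change after dosing. Days 2-4 are compared local with local, so the artefact would be absent there, start at Day 15 and persist at Day 29. That pattern resembles a delayed drug effect, and an offset in the other direction could hide a real one.

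Part 1 is the first evaluation of AXER-204 in humans (Protocol 5.3). Safety is part of its primary objective (6.1.1), and it is open-label without placebo (10.4.1). The DSMB reviews Part 1 safety before recommending the start of Part 2 (7.3.4). Nothing in the SAP normalises results between laboratories, pairs baseline and follow-up by laboratory, displays the laboratory source, or says whose reference range defines a shift or a PCS value.

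**Working it through.** **Step 1: trace of laboratory by visit (Part 1 hematology and chemistry).**

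| Visit | Laboratory | Source | Change from Day 1 baseline |
|---|---|---|---|
| Screening | Central | 14.1.5 | not used if a Day 1 value exists |
| Day 1 pre-dose | Local | Table 5 fn 10; 14.1.5 | baseline (SAP 8.8.3) |
| Days 2, 3, 4 | Local | Table 5 fn 10; 14.1.5 | local minus local |
| Days 15, 29 | Central | 14.1.5 | central minus local |

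Let b be the central-minus-local offset. The expected artefact in the mean change is 0 at Days 2-4 and b at Days 15 and 29. With the central Screening value as baseline it is 0 at Days 15 and 29 as well. Urinalysis is scheduled in Part 1 only at Screening and Day 29, both central, so its artefact is also 0. If an analyte is missing from the local Day 1 panel, the SAP rule falls back to the central Screening value. Baselines could therefore mix laboratories across analytes and subjects.

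**Step 2: size relative to sampling error.** The plan states no figure to reproduce. Inputs from the documents are cohorts of 6 and up to 24 subjects at about 5 sites. Inputs assumed here are b = 5-15% and a within-subject SD of change of 10%.

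The 95% half-width of a mean change is t(0.975, n-1) × SD / √n.
- Pooled, n=24: 2.069 × 10% / √24 = 4.2%. Ratios: 5/4.2 = 1.2 and 15/4.2 = 3.6.
- One cohort, n=6: 2.571 × 10% / √6 = 10.5%. Ratios: 5/10.5 = 0.5 and 15/10.5 = 1.4.

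**Step 3: how far this depends on the assumptions.**
- SD of change 20%: the pooled half-width doubles to 8.4%, so the pooled ratio is 0.6-1.8.
- Independent offsets of typical size b at 5 equally sized sites: the pooled offset is about b/√5 = 2.2-6.7%, or 0.5-1.6 pooled half-widths at an SD of 10%. The rest appears as extra noise.

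**Step 4: shift tables.** An illustrative simulation used a total SD of 1, a within-subject SD of 0.5 and one common range of ±1.96 SD, with the local laboratory reading lower by the offset. In-range-to-high shifts at Day 15 rise from 1.6% with no offset to 2.0%, 2.3% and 2.9% at offsets of 0.25, 0.5 and 1.0 SD. With the central Screening baseline they stay at about 1.6%. Shifts are thus less sensitive than means, and less still if each laboratory's own range is applied.

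**The case against.** **Part 1 analysis is descriptive and has other checks.** No inferential testing is planned (Protocol 15.3). Four dose levels from 3 to 200 mg give an internal check, because a laboratory offset has no reason to follow dose. All laboratory data are listed, so a reader could compare Screening with Days 15 and 29. Investigators review results and abnormal values are repeated (14.1.5). Escalation rests on clinical review, including AEs and SAEs, and available PK (7.3.3), not on mean-change tables. This stands, and it limits the consequence. It does not make the tabulated mean changes like for like. The dose check is also coarse at 6 subjects per cohort.

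**Day 1 is the better baseline in time.** Screening laboratory tests may be up to 28 days old (7.1.1) and may precede the washout of prohibited medication, which need only be complete before dosing (10.2). Replacing Day 1 could bring in withdrawal effects and break the time course from Days 2-4 to Days 15-29. This also stands. It is a reason to show both summaries rather than to replace one.

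**Wider readings a reader might infer.**
- *Part 2 has the same defect.* The sentence in Section 14.1.5 is not expressly limited to Part 1. However, the Part 2 counterpart, footnote 8 of Table 6, repeats the INR/PTT requirement and omits local processing. Part 2 has no Day 2, 3 or 4 visit, and Days 1 to 4 is how Section 11.1.2 labels the Part 1 in-clinic visit. Part 2 also has a randomized placebo arm. The documents support a request for clarification only.
- *All Part 1 laboratory tables are biased.* Urinalysis is not affected and Days 2-4 are not affected. Shift and new-onset PCS tables are largely protected if each laboratory's own range is used. The new-onset definition also looks at any pre-dose PCS value, although its denominator uses baseline.
- *A bias has been shown.* No offset is documented. The plan leaves one uncontrolled.

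**Conclusion.** The point holds for Part 1 hematology and clinical chemistry at Days 15 and 29, wherever a Day 1 pre-dose value exists. There, any offset between the local and central laboratories passes in full into the mean change, and Part 1 has no concurrent control to identify it.

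The size is unknown from the documents. Under an offset of 5-15% common to all sites and an SD of change of 10%, it is 1.2-3.6 times the pooled 95% half-width and 0.5-1.4 times the half-width of a single cohort. The upper pooled figure should not be read as the expected case. It needs all of about 5 site laboratories to be off by the same amount in the same direction, and a larger SD or differing offsets bring it down.

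This is an avoidable weakness in descriptive safety tables and a cheap improvement. It does not invalidate the Part 1 safety evaluation.

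**What to change.** In SAP 8.8.3, for Part 1:

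1. Add a laboratory-source flag (local or central) to the analysis dataset and the listings.
2. For hematology and chemistry at Days 15 and 29, summarise change and shift from the last pre-dose central value (Screening), shown beside the Day 1-based summary.
3. Keep the local Day 1 pre-dose value as the baseline for Days 2-4.
4. State that shifts and PCS values use the reference range of the laboratory that ran the sample.

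For Part 2, confirm in Protocol 14.1.5 that local processing on Days 1-4 applies to Part 1 only.

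**Cost.** No new samples are needed. The Screening baseline may be up to 28 days old and may precede washout, which is why both summaries should be shown. SAP 2.2 has Part 1 outputs produced at Part 1 lock, and SAP 2.3.2 already reports data from 23 Part 1 patients, so the change means a supplementary run of the Part 1 laboratory tables.
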